#### 5.3 Exclusion criteria

Patients with any of the following will be excluded from study enrolment:

- Inclusion criteria not met
- Angina/suspected myocardial infarction
- Were recruited to this study within 28 days of the current admission
- Could not be recruited to the study within a 16-hour period of initial assessment by a doctor
- Enrolment in a study of antimicrobial therapy of the illness for which the patient has been admitted.

## 6 STUDY PROCEDURES

#### 6.1 Entry to the study (Day 1)

Only patients who meet all of the inclusion and none of the exclusion criteria described in sections 5.2 and 5.3 will qualify to enter the study. The following procedures will be performed and recorded at baseline (Day 1):

#### 6.1.1 Identification of potential trial participants

Male or female patients with an acute respiratory illness or exacerbation of chronic cardio-pulmonary illness of recent onset ( $\leq$ 7 days (168 hours)), who are thought eligible by the admitting team (nursing and/or on-call medical staff on the Medical Admissions Unit), will be considered by the Study Nurse (or a Study Doctor) for inclusion in the study.

#### 6.1.2 Approach to potential trial participants

Potential research participants will only be approached by the Study Nurse or Study Doctor after they have been admitted and assessed by the nursing staff on the Medical Admissions Unit or another ward that admits patients with acute cardio-pulmonary conditions, normally after they have been clerked by the admitting doctor. The Study Nurse (or Study Doctor) may approach an accompanying relative or carer of a referred patient who can not give signed informed consent either because: (a) he/she is so breathless or confused that he/she is temporally unable to assimilate information regarding the study to judge whether to participate; or (b) the patient has pre-senile or senile dementia. In such cases, the Study Nurse or Study Doctor will seek informed Assent from either the patient's relative or a carer. The Study Nurse or Study Doctor will subsequently approach patients whose recovery enables them to provide signed informed consent.

#### 6.1.3 Recruitment

Patients who evidently satisfy the entry criteria will be asked by the Study Nurses or medical staff carrying out the study whether they would be willing to learn about it, with a view to taking part. An Information Sheet will be given to each patient (Appendix IV); Patients who are not known to be suffering from dementia but are too unwell to read the Information Sheet may be recruited to the study provided that they give signed informed consent after reading the Synopsis of the Patient Information Sheet (Appendix IVa). This possible event will be documented in the Case Report Form. The patient should be re-consented using the Patient Information Sheet (Appendix IV) when he/she is able to assimilate information regarding the study to judge whether to continue. If the patient recovers and withdraws his/her consent, then all laboratory specimens will be destroyed and the patient will be excluded from the study. A modified version of the Information Sheet (Appendix V) will be given an accompanying relative or carer of a referred patient who can not give signed informed consent either because: (a) he/she is so sick (breathless or confused) that he/she is temporally unable to assimilate information regarding the study to judge whether to participate; or (b) the patient has presenile or senile dementia). Potential trial participants will be informed that their participation is entirely voluntary, and that their medical care will not be adversely affected in any way if they decide not to participate. Consent to participate in the study will be obtained either at the end of the discussion, or at some point up to 16 hours after initial assessment by the doctor on the Medical Admissions Unit when there has been a chance for the patient to reflect on all the relevant issues (Appendix VI). All prospective trial participants who are considered capable of providing signed informed consent by the nursing and/or medical team providing clinical care will be required to give written informed consent before any trial related assessments or procedures are conducted. The Study Nurse or Study Doctor will only seek informed Assent (Appendix VII) from either a relative or a carer for subjects who are considered unable to give written informed consent. All subjects will subsequently be screened for eligibility (Inclusion/Exclusion criteria check) and recruited only if all criteria are satisfied.

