*Patients who are incapable of providing consent* The Study Nurses or medical staff taking part in the study may additionally approach an accompanying relative, or a carer, of patients who can not give signed informed consent either because: (a) they are so breathless or confused that they are temporally unable to assimilate information regarding the study to judge whether to participate; or (b) the patient has pre-senile or senile dementia. In such cases, the study nurse or study doctor will seek informed Assent from either the patient's relative or a carer. The clinical investigators or their deputies must also explain to relatives or carer that they are completely free to refuse assent to enter the study or to withdraw it at any time for any reason, without incurring any penalty or loss of any benefit to which the patient is otherwise entitled. Appropriate forms for

documenting signed informed assent will be provided by the Principal Investigator. The clinical investigator, or his/her designee must document in the case report form that assent was obtained BEFORE any trial specific procedures are performed on the subject. The study nurse or study doctor will subsequently approach patients whose recovery enables them to provide signed informed consent.

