#### 6.1.13 Randomisation and Trial Identification Numbers

Patients in each centre will be randomly allocated, using computer generated randomisation codes stratified by centre, to one of three diagnostic study groups:

Group 1: Rapid near patient diagnostic tests (influenza and pneumococcus),

Group 2: Rapid molecular tests (influenza & RSV), plus laboratory pneumococcal antigen testing, and Group 3: Traditional 'laboratory culture' (influenza, RSV, and *S. pneumoniae*)]

The randomisation code (i.e., whether in Group 1, 2, or 3) will be included in sequentially numbered study packs that will be stored at each hospital (Leicester Royal Infirmary, Glenfield Hospital, and Leicester General Hospital). The Packs will be labelled as follows:

1-0001, etc, (Leicester Royal Infirmary site One)

**2**-0001, etc, (Glenfield Hospital siteTwo)

**3**-0001, etc, (Leicester General Hospital site Three) which correspond to the Trial Identification Numbers allocated to participants at each study site.

The randomisation codes will be generated by the Department of Health Sciences, University of Leicester. The randomisation code will not be known by the Study Nurse until after the patient has signed the Patient Informed Consent Form. Only then will the study pack containing details of randomisation be opened.

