#### 2. NASOPHARYNGEAL SPECIMENS

One (1) nasal, and one (1) nose and throat swab sample will be collected from all study participants. (See Appendix VIII) The nasal swab can be found in the The Quidel QuickVue Influenza A+B test kit, which is included in the sequentially numbered study packs. Similarly, nose and throat swabs for collection of nasopharyngeal specimens will be found in the participant's study pack. They will be used as follows:

• **GROUP 1 ONLY**: The swab in the Quidel QuickVue Influenza A+B test kit will be used in *one nostril only*, specifically to collect a nasal sample – for rapid near patient testing, in the MAU/ward, of participants in Group 1.

Patients randomised to Group 1 will have near patient tests for influenza A and B antigen done by the study nurse in an area of the MAU/ward where clinical tests such as urinalysis are done routinely. The instructions for collecting the Quidel QuickVue nasal sample and doing all tests are provided in Appendix IX. On completion of the test the Study nurse will:

- (a) Record the test result in the CRF;
- (b) Inform the team (i.e., the responsible nurse and/or doctor) that is providing clinical care of the patient of the rapid near patient test result (i) verbally; and (ii) by insertion of an adhesive label in the notes. The clinical team should be told that a negative test does not exclude infection with influenza A or B.
- (c) Document in the CRF the time that the team was informed, and who was told.
- **GROUPS 1, 2, and 3**: The nose and throat swabs for the molecular tests and traditional tissue culture studies (for influenza and RSV) will be used to swab the throat and *the opposite nostril* (i.e., ONE nostril only) to that used previously and placed in virus transport medium. The instructions for collecting the nose and throat sample are provided in Appendix VIII. The nose and throat sample will be collected from ALL study participants, specifically for:
  - Prompt, conventional viral culture (Groups 1, 2, and 3);
  - Prompt, rapid molecular testing for influenza A and B and RSV A and B (Group 2);
  - Deferred, molecular testing for influenza A and B and RSV A and B (Groups 1 and 3);
  - Deferred Quidel QuickVue test for influenza A and B (Groups 1 and 2)
  - Possible future tests for other respiratory pathogens of stored specimens, if tests for influenza, RSV, and *S. pneumoniae* are negative.

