#### 7.6 Statistical analysis

All analyses for both process and clinical outcomes will be based on Intention to Treat (ITT) analyses.

Impact of test result on prescribing The time to prescription of `narrow spectrum', `oral antibiotics' or `no antibiotics' between the three groups will be assessed using survival analysis techniques, whilst the use of neuraminidase inhibitors in those with influenza will be assessed using  $\chi^2$  tests, together with 95% CIs. Further analyses to allow for potential differences in patient demographics and baseline clinical characteristics between the three diagnostic test groups, and not allowed by stratification, will make use of cox proportional hazards regression modelling in the case of time to appropriate prescribing and logistic regression techniques in the case of neuraminidase inhibitors.

*Length of hospital stay* Length of hospital stay in the three diagnostic groups will initially be compared using non-parametric methods. Further analyses to allow for potential differences in patient demographics and baseline clinical characteristics between the three diagnostic test groups, and not allowed by stratification, will make use of generalised linear models in order to accommodate any skewness in the data.

*Mortality rates* Mortality rates between the three diagnostic testing groups will be compared by means of a Log-Rank Test and Kaplan-Meier survival curves. Adjustment for potential differences in patient demographics and baseline clinical characteristics between the three diagnostic test groups, and not allowed by stratification, will make use of Cox proportional hazards regression methods.

*Diagnostic accuracy* Sensitivity, specificity, positive predictive value of molecular and near patient diagnostic tests in comparison to traditional laboratory methods will be calculated together with 95% CIs. Heterogeneity in the sensitivity and specificity with respect to patient demographics and baseline clinical characteristics will be explored as secondary analyses using patient defined sub-groups.

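### Section 6.1.3 excludes already randomised patients who decline at re-consent and destroys their specimens, which conflicts with the intention-to-treat statement in Section 7.6

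*Protocol*

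**What the plan says.** Section 6.1.3 opens an entry route for patients not known to have dementia who are "too unwell to read the Information Sheet may be recruited to the study provided that they give signed informed consent after reading the Synopsis". Later, "The patient should be re-consented using the Patient Information Sheet (Appendix IV) when he/she is able to assimilate information". The consequence of declining follows directly: "If the patient recovers and withdraws his/her consent, then all laboratory specimens will be destroyed and the patient will be excluded from the study".

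Randomisation comes before that second decision. Section 6.1.13 says of the allocation: "The randomisation code will not be known by the Study Nurse until after the patient has signed the Patient Informed Consent Form". It continues: "Only then will the study pack containing details of randomisation be opened". The baseline procedures in the protocol synopsis list randomisation on Day 1. The schedule of assessments places consent upon recovery in the column for Days 2 to 10.

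Section 7.6, like the protocol synopsis, states: "All analyses for both process and clinical outcomes will be based on Intention to Treat (ITT) analyses". Section 7.3 adds that evaluations will use study groups made up of everyone investigated under each strategy. Section 4.1 says that every patient who enters will eventually have every test.

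For patients entered on a relative's or carer's assent, Section 3.3 says only: "The study nurse or study doctor will subsequently approach patients whose recovery enables them to provide signed informed consent". It states no consequence of declining. Sections 3.3 and 6.1.4 also allow withdrawal at any time without saying what then happens to data or specimens.

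**The concern.** Intention to treat keeps each randomised patient in the group to which chance assigned them. A rule that removes some of them later, on the strength of something that happens after allocation, gives up that protection. Here the event is a decision made after some recovery. A patient who dies early or never regains capacity cannot leave by this route.

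The trial is open. By the time of re-consent the study nurse knows the group, and in Group 1 the nurse's task has been to "Inform the team (i.e., the responsible nurse and/or doctor) that is providing clinical care of the patient of the rapid near patient test result". If willingness to continue differs between groups, the patients left in each group are no longer comparable.

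Mortality and length of stay are the outcomes exposed. Mortality matters particularly because the protocol hypothesises that streamlined prescribing does no harm (Section 2.1, item 7) and sets up special reporting of deaths (Section 10.4).

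The specimen rule adds a second problem. Infection status defines several endpoint populations, and it rests on tests that some groups have promptly and others have only later.

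**Working it through.** **Order of events.** Short-form consent is signed, the pack is opened, samples are taken, and rapid results are released in Groups 1 and 2. The patient then regains capacity, is asked again, and may decline and be excluded. The exclusion therefore follows randomisation. Nothing in Section 6.1.3 or 7.6 says that these patients stay in the intention-to-treat set, or separates stopping procedures from withdrawing data.

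**Specimens.** Sections 6.1.14 and 7.3, set side by side:

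| Test | Group 1 | Group 2 | Group 3 |
|---|---|---|---|
| PCR (influenza, RSV) | deferred | prompt | deferred |
| Urine pneumococcal antigen | bedside | prompt, laboratory | deferred |
| Viral, blood and sputum culture | yes | yes | yes |

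Section 9 schedules PCR and stored-urine testing in batches, mostly in the summer after each season, whereas re-consent falls within days of admission. Destruction would therefore usually come before deferred testing. A decliner in Group 2 would have PCR and antigen results. One in Group 1 would lack PCR, and one in Group 3 would lack both. This matters even if exclusion is read as ending procedures only, with data kept.

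**Size.** The protocol gives no figure to reproduce and no rates, so every rate below is an assumption.

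*Length of stay.* Let f be the share of a group entering on the short-form sheet, w the share of those who decline, and e = f × w the share of the group removed. Let D be the number of days by which the removed patients' mean stay falls below the group mean. Removal raises the observed mean by e × D / (1 − e).

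- Assumed ranges: f = 5–20%; w = 10–30% in a rapid-test group and 10% in Group 3; D = 3–6 days.
- Most extreme case: f = 20%, w = 30% v 10%, D = 6. Then e = 0.06 v 0.02.
- Shifts: 0.06 × 6 / 0.94 = 0.383 day; 0.02 × 6 / 0.98 = 0.122 day. The spurious difference is 0.26 day.
- Patients removed, with 2752 / 3 = 917 per group: 917 × 0.06 = 55 and 917 × 0.02 = 18.
- Mild case: f = 5%, w = 20% v 10%, D = 3. Then 0.01 × 3 / 0.99 − 0.005 × 3 / 0.995 = 0.015 day.
- Equal w and equal D: zero.
- If removed patients stay longer than average, D is negative and the sign reverses. The assumed range is thus −0.26 to +0.26 day, against the 1-day difference in Section 7.4.

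*Mortality.* Let m be true 28-day mortality and q the mortality among those removed. Observed mortality is (m − e × q) / (1 − e).

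- Assume m = 10% in both groups. With q = 0 and e = 2% v 6%: 0.10 / 0.98 = 10.2% and 0.10 / 0.94 = 10.6%, a spurious 0.4 percentage points.
- With q = 10%, observed mortality stays at 10% in both groups.

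**The case against.** The strongest reply has four parts.

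**Consent.** These patients never agreed on full information, so destroying specimens when they decline may be what an ethics committee requires. The information sheets and consent forms (Appendices IV to VII) are not in the text available and may say more about data. This stands as a reason to make any change subject to ethics approval. It does not reconcile Section 6.1.3 with Section 7.6.

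**Wording.** Exclusion from the study need not mean that collected data are deleted. That is fair: the protocol does not say they are. It also does not say they are kept, and the uneven loss of deferred tests remains on either reading.

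**A later analysis plan could define the population.** It could settle the data question, but it could not recover destroyed specimens.

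**Size.** The effect is small, and 20% dropout is already allowed for. The size point stands. The dropout allowance protects power, not comparability.

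Several stronger readings are tempting, and the text does not support them:

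- *That exclusion depends on the allocated group.* The trigger is the patient's decision. Allocation is merely known to staff by then.
- *That everyone removed is a survivor with a short stay.* Recovery here means regained capacity, possibly early. Such a patient may still die within 28 days, and someone too ill to read at admission may stay longer than average.
- *That Group 3 patients have received nothing.* Identical samples are taken, and culture and Gram stain results are reported (Sections 6.1.14 and 6.2.1).
- *That the rule reaches assent entrants.* In context the sentence covers short-form entrants. Their number is unknown.
- *That losses cannot be traced.* The CRF records short-form entry, packs are numbered in sequence, and enrolment logs list every entrant.

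**Conclusion.** The point holds in a limited form. Section 6.1.3 states a rule for short-form entrants that removes randomised patients after allocation, by a route open only to those well enough to decide. The protocol does not reconcile this with intention to treat or with study groups comprising everyone investigated. Specimen destruction falls unevenly because PCR is deferred in Groups 1 and 3 and urine antigen in Group 3.

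The bias is probably small. Under the assumed rates it is at most about a quarter of a day in mean length of stay, in either direction, and about 0.4 percentage points of mortality if all those removed survive. There is no between-group bias if refusals have the same rate and profile in each group. These figures rest wholly on assumed entry and refusal rates. The change is worth making because it is cheap and brings the consent rule into line with the stated analysis.

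**What to change.** Replace automatic exclusion with a choice recorded at re-consent, subject to ethics approval:

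1. No further samples, visits or questionnaires.
2. Specimens destroyed if the patient asks.
3. Data collected up to that point kept, together with length of stay and vital status from hospital records, where the patient permits.

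Apply the same rule to short-form, assent and full-consent entrants. State in Section 7.6 that permitted data stay in the intention-to-treat set. Report every randomised patient, and every withdrawal with its level, by group.

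The cost is an ethics amendment and one CRF item. Patients who refuse all use of their data are still lost to the analysis, but they are counted by group.

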#### 6.1.4 Written informed consent/assent

Consent or Assent will be required to before any trial related assessments or procedures are conducted. Consent or Assent will be sought following discussion with the nursing and/or medical team providing clinical care about the patient's status. Subjects will be screened for eligibility (Inclusion/ Exclusion criteria check) and recruited only if all criteria are satisfied.

A Study Nurse or Doctor (after appropriate training), will obtain written informed consent from all individuals who are capable of providing consent prior to entry to the study, after adequate explanation of the aims, methods, objectives, and potential hazards of the study, including any discomfort it may entail. Such individuals will be told that they are completely free to refuse to enter the study or to withdraw from it at any

time for any reason, without incurring any penalty or loss of any benefit to which they are otherwise entitled. This information will be supplemented with a Patient Information Sheet, which provides written information concerning the above (Appendix IV). The Patient Information Sheet will be given to the research participants to be kept for reference. Subjects will be given every opportunity to clarify any points they do not understand and if necessary ask for additional information. Signed informed consent to participate in the study will be recorded on a Consent Form (Appendix VI) either at the end of the discussion, or at some point to 16 hours after initial assessment by the doctor on the Medical Admissions Unit when there has been a chance for the patient to reflect on all the relevant issues. Signed Informed Consent Forms must be kept on file by the Investigators in the Study Coordinating Centre (Infectious Diseases Laboratory, Leicester Royal Infirmary) and the collection of informed consent and transfer of the document to the Coordinating Centre must be documented in the CRF. The clinical investigator, or his/her designee (Research Nurses/Research Doctor taking part in the study) must document in the case report form that informed consent was obtained BEFORE any trial specific procedures are performed on the subject.

Signed informed Assent (See Appendix VII) should be obtained from a relative or carer of any patient who is incapable of providing consent, either because: (a) he/she is so breathless or confused that he/she is temporally unable to assimilate information regarding the study to judge whether to participate; or (b) the patient has pre-senile or senile dementia. Relatives and carers should be given the same information about the study (Information Sheet, See Appendix V) and opportunities to clarify any points and time to reflect on participation as given to patients able to give consent. The clinical investigators or their deputies must also explain to relatives or carer that they are completely free to refuse assent to enter the study or to withdraw it at any time for any reason, without incurring any penalty or loss of any benefit to which the patient is otherwise entitled. Appropriate forms for documenting signed informed assent (Appendix VII) will be provided by the Principal Investigator. The clinical investigator, or his/her designee must document in the case report form that assent was obtained BEFORE any trial specific procedures are performed on the subject. The study nurse or study doctor will subsequently approach patients whose recovery enables them to provide signed informed consent.

